Title of Study: A Double-Blind, Randomized, Placebo Controlled, Clinical Trial of an Antiplaque Chewing Gum (30 mg) - Phase 2 Proof of Concept in a Generally Healthy Patient Population	
Study Center: Salus Research [name]	
Principal Investigator: [name], MPA	
Sub-Investigator: [name], RDH, BSEd, MS (Examiner)	
Study Period (years): Estimated date first subject enrolled: August 2016 Estimated date last subject completed: August 2016	Phase of development: 2
Objectives: Primary: 
• To assess the safety and tolerability of KSL-W (30 mg dose) delivered in a chewing gum formulation compared to a placebo gum formulation Secondary: 
• To assess the proof of concept change in plaque regrowth from baseline in the Quigley Hein-Turesky Plaque Index (QHT) of KSL-W (30 mg dose) compared to a placebo gum formulation• To evaluate the proof of concept of KSL-W (30 mg) in change in plaque regrowth based on sub-scores from specific regions of the upper jaw, lower jaw, buccal and lingual surface based on the QHT	
Methodology: This study is a Phase 2 two-armed placebo-controlled, double-blind, randomized (1:1) multiple dose, single center study to evaluate the safety and proof of concept of 30 mg KSL-W administered in a chewing gum formulation 3 times per day over 4 treatment days. Oral hygiene (teeth brushing, flossing and/or mouth wash rinse) is prohibited throughout the trial beginning 12 to 16 hours before both the screening and Baseline (Day 0) visits, during the 4 days of treatment (Days 0, 1, 2, and 3) and ending after the periodontal examination and plaque assessment on Day 4. The ability of KSL-W to reduce existing supragingival plaque will be assessed. The oral soft (OST) and oral hard tissues (OHT) will be examined. Changes from baseline, such as soft tissue erythema, ulceration and sloughing, will be noted.	
Estimated Number of Subjects Screened: 35	
Estimated Number of Subjects Enrolled: 26	

Number of Subjects (planned): 24

A sample size of at least 12 subjects per study arm (KSL-W, Placebo) yields at least a posterior 94% chance of observing any KSL-W improvement in the sample mean QHT scores, and at least an 81% posterior chance (given that an improvement was observed) that the projected sample size for a similar, later phase, confirmatory study, using a 2-tailed $p = 0.05$, power = 90% criterion, is no more than 100 per study arm. This is based on the results of the phase 2a trial at Day 14, where for the 30 mg dose the observed QHT mean change from baseline was -0.31 with $n = 7$ subjects, and for the placebo subjects the QHT mean change from baseline was -0.03 with $n = 16$. The observed QHT error standard deviation was 0.22. It was assumed that these Day 14 results from phase 2a apply to this study having 4 days treatment.

Diagnosis and Main Criteria for Inclusion/Exclusion:

Male and female subjects between the ages of 18 and 64 (inclusive at the time of screening) who are in good health with a minimum of 20 natural teeth will participate in this study.

Investigational Product Dosage, Schedule, and Mode of Administration:

Subjects will receive 30 mg oral doses of KSL-W or placebo chewing gum in tablet form. After a dental examination including teeth polishing, subjects will receive the first dose under supervision in the clinic. The 11 doses will be self-administered and unsupervised. The maximum dose of KSL-W in a 24 hour period is three 30 mg chewing gum tablets (90 mg total). Each dose consists of 1 piece of gum (tablet). The gum will be chewed for 20 minutes balanced as equally as possible between both sides of the mouth. The gum will be chewed preferably after a meal or in 4-6 hour intervals three times a day for a total of 4 days.

Duration of Treatment: Four days

Reference Therapy, Dosage, Schedule, and Mode of Administration:

This is a double-blind, two-armed, randomized placebo-controlled study. The KSL-W and placebo tablets will be identical in appearance.

Criteria for Evaluation:

Safety:

Occurrence of local oral mucosal reactions, systemic reactions and serious total body reactions will be assessed. In addition, physical examinations and vital signs will be taken before treatment and at the end of the study.

Proof of Concept (Efficacy/Effectiveness):

Changes from baseline in the Quigley-Hein Turesky Plaque Index (QHT) will be calculated as whole mouth scores. Average scores of selected subsets of measurements sites (interproximal, facial, lingual, maxillary, mandibular, and posterior) will be calculated as exploratory endpoints.

Statistical Methods:

Two evaluators will be used for this study and each subject's randomly assigned evaluator will stay with that subject throughout the study. The randomization to the study arm (KSL-W, placebo) will be 1:1. All adverse events (AE) will be presented in by-subject data listings. Treatment-emergent AEs will be tabulated where treatment-emergent is defined as any AE that occurs after administration of the first dose of study treatment or any medical or dental condition that is present at baseline but worsens in intensity subsequent to the administration of the first dose of study treatment. In addition to the subject listings, summaries by study arm, noting severity and relationship to study treatment, will include AE incidence proportions and rates by system organ class (SOC) and by preferred term (PT) within SOC. Incidence rates (in events per subject week) will be estimated as the number of treatment emergent AEs divided by the total number of patient-weeks. AE incidence proportion will be estimated based on the number of subjects having at least one AE of a particular type divided by the number of subjects exposed.

Data from physical examinations and vital signs will be summarized for each evaluation time point. Any abnormal physical examination findings noted at the end-of-study exam on Day 4 will be tabulated as a listing. For vital signs, change from baseline to the end-of-study evaluation time points will be summarized.

Two proof of concept (efficacy) endpoints will be assessed. The first, will use the QHT whole mouth scores from the full analysis set (FAS) and will be based on the mean change from baseline to Day 4. The QHT whole mouth average will be the average of scores only from surfaces evaluable for QHT. The QHT score is based on each subject having at least 20 teeth with 6 evaluable surfaces per tooth.

An analysis of covariance (ANCOVA) model will be used to compare 30 mg KSL-W with placebo. The model will include the baseline score and study arm (KSL-W, placebo). Sensitivity assessments will be employed to determine whether the effects of treatment on the slope of the baseline covariate, and the effect of evaluator on the treatment placebo comparison can be ignored.

While a formal p-value comparison based on the final primary ANCOVA model will be generated and summarized, this will not be the primary evaluation since this study has not been powered for detection of a minimally clinically important improvement in QHT. The primary proof of concept summaries for this study will include the estimated difference, KSL-W minus placebo, in the mean (QHT) change from baseline, and the estimated error standard deviation from the primary ANCOVA model. This information will be critical to assess the chances for a successful demonstration of KSL-W efficacy in future phase 3 studies utilizing QHT evaluations, as a function of the sample size of these studies.

Similar ANCOVA models will be used for the per protocol (PP) population, and secondary mean scores (FAS and PP), and the results from each model will be summarized.

The second proof of efficacy endpoint will assess the reduction in plaque based on sub-scores from specific regions of the upper jaw, lower jaw, buccal and lingual surface.

Descriptive and inferential summaries for FAS and PP will be presented for all scores by study arm overall, and by study arm and evaluator. The summaries will include the mean, standard error, minimum, 25th percentile, median, 75th percentile, and maximum, for baseline, Day 4, and change from baseline to Day 4. P-values will be given for study arm comparisons but will not be adjusted for multiple comparisons.

Missing data will not be imputed. A missing QHT score will occur if there are insufficient numbers of surfaces evaluable for QHT. A subject will be considered lost to follow-up if their Day 4 morning evaluation occurs more than 24 hours after the scheduled time.

3. Table of Contents, List of Tables, and List of Figures

[figure not shown]
Table of Contents

1.	Title Page	1
2.	Synopsis	7
3.	Table of Contents, List of Tables, and List of Figures	10
4.	List of Abbreviations and Definitions of Terms	16
5.	Introduction	18
5.1	Military Relevance	18
5.2	Rationale for Study	18
5.3	Background	18
5.4	Name and Description of the Investigational Product	20

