- The first chew will be administered under supervision in the clinic. The subject will be instructed to chew one tablet of gum for 20 minutes. Chewing should be balanced as equally as possible between both sides of the mouth.
- After chewing the gum for the designated time, the subject will be given a used product bag to store the chewed gum. The evaluator will inform the subject to label this bag with the time and date of the chew.
- After the chewing gum is stored in the used product bag, the subject will complete the start and stop times for chewing gum on the electronic diary information system (ePRO). The subject will enter this information while in the clinic.
- The study drug will be dispensed for unsupervised use. The subject will receive:
 - 13 gum tablets for their unsupervised use along with 13 individual used product collection bags.
 - Subjects will be given instructions for chewing the gum.
 - a. The gum will be chewed for 20 minutes preferably after a meal or every 4 to 6 hours (3 times a day). Chewing will be balanced as equally as possible between both sides of the mouth for a maximum of 3 chews per day.
 - b. After completing each 20 minute chew, subjects will store the used gum in the used product collection bags provided to them.
 - c. Subjects will label each used product collection bag with the date and time of chew. (A separate bag will be used for each chew).
 - d. After each chew, subjects will record the start and stop time of the chew on the electronic diary information system - ePRO (Instructions provided in [Appendix D](#))
 - e. Subjects will be informed that they must bring all of the used product collection bags back to the clinic for Visit 3
- Subjects will be told that no oral hygiene procedures of any kind (teeth brushing, flossing or mouth wash rinse) will be allowed while on study treatment (Day 0, 1, 2, 3 and 4).
- AEs from first chew will be collected.
- Concomitant medication will be recorded.

9.1.3 Unsupervised Treatment, Study Days 0, 1, 2, and 3

After the first supervised chew is completed, the subjects will be released from the clinic. There will be a total of 11 unsupervised, self-administered chews. The subjects will chew one tablet of the gum (study drug) for 20 minutes every 4 to 6 hours, preferably after a meal, for a maximum of 3 chews per day according to the schedule in [Table 6](#).

Table 6: Schedule for Unsupervised Chews:

Time ^a	Day 0	Day 1	Day 2	Day 3
After Breakfast ^b	N/A	1	1	1

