After Lunch	1	1	1	1
After Dinner	1	1	1	1
Total Chews per Day	2	3	3	3

^a Gum will be chewed for 20 minutes preferably after a meal or every 4 to 6 hours for a maximum of 3 chews per day. Chewing will be balanced as equally as possible between both sides of the mouth.

^b First chew takes place in the clinic.

After completing each 20 minute chew, the subject will store the used gum in the used product collection bags provided to them. The subject will record the date and time of chew on the individual collection bags as instructed. A separate bag will be used for each chew. Subjects will record their chewing gum start and stop times on the electronic diary system (ePRO) after each chew.

9.1.4 Treatment, Study Day 4 – Visit 3

After 4 days of treatment, subjects will return to the clinic for Visit 3. The following procedures will occur at Visit 3:

- Subjects will return all used product bags and any unused product. Site Staff will collect used/unused product bags.
- Vital signs (diastolic and systolic blood pressures, heart rate, respiration rate and temperature) will be measured.
- A brief, symptom-oriented physical examination will be performed
- Females of child-bearing potential will take a urine pregnancy test
- Subjects will be asked to verify that he/she has refrained from all oral hygiene procedures (teeth brushing, flossing or mouth wash rinse) since their last chew.
- An intraoral exam (OST and OHT) will be performed.
- Supragingival plaque will be assessed using the QHT. (A red, food dye will be used to disclose plaque deposits on the teeth).
- AEs will be assessed.
- Concomitant medications will be recorded.

- Subject will be discharged from the study. (Subject will be allowed to brush their teeth just prior to leaving the research center is discharged from the study.)

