12.8 Selection of Subjects to be Included in Analyses

The Full Analysis Set (FAS) is defined as all randomized subjects having Baseline and Day 4 QHT evaluations, with the Day 4 evaluation occurring on the morning following the last chewing gum treatment from the previous day. The FAS population will be analyzed according to their randomized treatment assignment.

The Per Protocol Population (PP) is a subset of FAS and consists of all subjects with no major protocol violations such as: failure to obtain valid informed consent, accidental distribution of incorrect study medication, not following the inclusion/exclusion criteria, evidence that study medication was not taken, and the performance of oral hygiene other than chewing the study gum during the study period. Analysis of the PP will be according to the treatment actually received by the subject.

The Safety Population consists of all randomized subjects receiving at least one dose of study medication, and summarized on the basis of treatment received. All AE summaries will be based on the safety population.

13 Direct Access to Source Data/Documents

Subjects will be identified on eCRFs by a unique subject identification number and on source documents by name and date of birth. No personal identifier will be used in any publication or communication used to support this research study. The subject identification number will be used if it becomes necessary to identify data specific to a single subject. Representatives of USAMRMC, the sponsor's representative, the IRB of Record and/or the USAMRMC ORP, and the FDA are eligible to review medical and research records related to this study as a part of their responsibility to protect human subjects in clinical research. Personal identifiers will be removed from photocopied medical and research records.

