6.1. Data Handling Conventions

6.1.1. Study Analysis Populations

The Safety Population consists of all subjects receiving at least one dose of study medication. These will most likely be randomized subjects receiving study therapy at Visit 3 (Day 0). The safety population will be analyzed according to the treatment actually received (KSL-W or placebo).

The Full Analysis Set (FAS) is defined as all randomized subjects having Baseline and Day 4 QHT evaluations, with the Day 4 evaluation occurring on the morning following the last chewing gum treatment from the previous day. The FAS population will be analyzed according to their randomized treatment assignment. A randomized subject with a missing Day 4 QHT whole mouth score will not have this score imputed, and will not be in the FAS cohort.

The Per Protocol Population (PP) is a subset of FAS and consists of all subjects with no major protocol violations itemized as follows: failure to obtain valid informed consent, accidental distribution of incorrect study medication, not following the inclusion/exclusion criteria, evidence that study medication was not taken, and the performance of oral hygiene other than chewing the study gum was during the study period, Day 4 evaluation performed later than on the morning following the last chewing gum treatment from the previous day. Analysis of the PP will be according to the treatment actually received by the subject.

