6.1.2. Study Exposure

The baseline visit will be at Visit 3, Day 0, and the first dose of the study medication will be administered after randomization, determination of the baseline QHT score, and tooth polishing. The study exposure, in days, will be measured from Day 0 (date of randomization) to the last day

the subject was in the study. For subjects completing Visit 4, Day 4, the exposure will be 4 days (counting Day 0), regardless of whether the subject took any of the self-administered treatment. For early withdrawal subjects the study exposure will be from Day 0 to (and including) the subject's last day when the subject informs the study site of their early withdrawal. If the subject is lost to follow-up, the study site personnel will attempt to contact the subject to determine the day when they stopped study participation, and any adverse events that occurred during their self-administration time. Randomized subjects who are lost to follow-up and who are unable to be contacted will be assigned one day of study exposure, namely Day 0.

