11.2. Table Shells

TREF01

Subject Disposition

	Total	KSL-W	Placebo
Number Screened	xx		
Number Randomized	xx	xx	
Number Receiving Study Drug	xx	xx	
End of Study Status			
Number (%)* Completing Study	xx (%)	xx (%)	xx (%)
Number (%) with Early Discontinuation	xx (%)	xx (%)	xx (%)
Reason for Early Discontinuation			
Screening failure			
Adverse Event			
Lost to Follow-up			
Terminated by Principal Investigator			
Major Protocol Deviation/Deviation			
Subject requested to be withdrawn			
Sponsor decision to withdrawal	xx		xx

*(%) = percentage of those randomized, within total and each study arm

Subject Listing: LREF01, LREF12, LREF21b, LREF13

TREF02				
Analysis Populations				
		Total	KSL-W	Placebo
Number in Safety Population*		xx	xx (%)	xx (%)
Number in Full Analysis Set**		xx	xx (%)	xx (%)
Number in Per-Protocol Population***		xx	xx (%)	xx (%)

(%) = Percent of total

*Subjects receiving at least one dose of study therapy, analyzed according to the therapy received

**Subjects having a valid QHT evaluation at Study Days 1 and 4, analyzed as randomized

***Subjects in the Full Analysis Set with no major protocol deviations (see table TREF15 for a summary of major protocol deviations)

Subject Listing LREF12, LREF21b, LREF18

number screened: ENROLLMENT.ICFDT pg 2 eCRF

number randomized: RAND.RANDYN pg 36 eCRF

number in Safety pop: DRUGADMIN.DISPSCYN pg 46 eCRF

Number in Per-Protocol Population: from protocol dev. pg 101 eCRF, and a list of subjects with no major protocol Deviations

TREF03.1

Demographic Assessments

Safety Population: KSL-W (N=xx), Placebo (N=xx)

	KSL-W	Placebo	Total
Age (years)			
mean (std. dev)	xx.x (x.x)
Minimum, Median, Maximum

Gender, n (%)			
male	xx (xx)
female
unknown (not given)
Ethnicity, n (%)			
Hispanic or Latino	Xx (XX) (%)
Not Hispanic or Latino
Not reported, Unknown

Race, n (%)			
White	
Native Hawaiian, Other Pacific Islander
Black or African American
Asian
Other

Percentages may not add up due to rounding

Subject listing: LREF01

(TREF03.2 FAS, TREF03.3 Per-Protocol Population)

From Enrollment, pg 2 eCRF

TREF04.1

Medical History, Urine Drug Screen

Safety Population: KSL-W (N=xx), Placebo (N=xx)

		KSL-W	Placebo	Total
Does the subject have any relevant medical history? (past/concomitant diseases or surgeries)				
Yes*		n (%)	n (%)	
No		n (%)	n (%)	
Not collected		n (%)	n (%)	

Was Urine Drug Screen Performed?

Yes		n (%)	n (%)	
	Result			
	positive	n (% of yes)	n (% of yes)	

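### Both synopses call a subject lost to follow-up for being examined more than 24 hours late, which conflicts with the SAP body and would miscount disposition if applied as written

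*Protocol*

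**What the plan says.** The Statistical Methods part of both synopses (protocol section 2, SAP section 1) ends its short paragraph on missing data with: "A subject will be considered lost to follow-up if their Day 4 morning evaluation occurs more than 24 hours after the scheduled time". Neither document defines loss to follow-up anywhere else, and neither defines a completer by the timing of the visit.

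The other relevant text is as follows.

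- **Dosing is over before the visit.** Protocol 9.1 has one supervised chew, and then "There will be a total of 11 unsupervised, self-administered chews", all on Days 0 to 3 (protocol Table 6). The final visit comes afterwards: "After 4 days of treatment, subjects will return to the clinic for Visit 3". The SAP numbers this visit 4.
- **Exposure, SAP 6.1.2.** Site staff have to trace a lost subject and establish when that person left the trial: "If the subject is lost to follow-up, the study site personnel will attempt to contact the subject to determine the day when they stopped study". A lost subject who cannot be reached is given one day. A subject who completes the Day 4 visit is given 4 days, with no limit on lateness.
- **Per-protocol set, SAP 6.1.1.** The major violations include "Day 4 evaluation performed later than on the morning following the last chewing gum treatment from the previous day". TREF18 has a row for the same event.
- **Full analysis set, protocol 12.8 and SAP 6.1.1.** Baseline and Day 4 scores are required, "with the Day 4 evaluation occurring on the morning following the last chewing gum treatment from the previous day".
- **Disposition, SAP 11.2, TREF01.** Randomized subjects either complete the study or fall under "Number (%) with Early Discontinuation". Loss to follow-up is one of the rows under "Reason for Early Discontinuation".

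**The concern.** Loss to follow-up normally means that the subject's outcome is unknown. Here the rule is triggered by an evaluation that occurs, only late. That subject has been seen: vital signs, the oral examination, adverse events and a plaque score are all obtained at the visit. Read literally, the sentence also fails to cover the subject who never returns, since no evaluation then occurs.

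Safety and tolerability is the primary objective, and readers use discontinuation counts to judge tolerability. A scheduling delay should not look like a drop-out. Because the plan gives one event several labels, two programmers could each follow a stated passage and produce different disposition tables.

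**Working it through.** There is no design figure to reproduce. The check is a comparison of passages followed by simple proportions.

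**Step 1. One event, several labels.** Take a subject who completes all 1 + 11 = 12 chews on Days 0 to 3 and is examined 25 hours after the scheduled Day 4 time, that is, on Day 5.

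| Place | Treatment of this subject |
|---|---|
| Both synopses | Lost to follow-up |
| SAP 6.1.1, per-protocol set | Major protocol violation |
| TREF18 | A deviation row, tabulated within the FAS |
| FAS definition | Outside the FAS, because the evaluation was not on the morning after the last chew |
| SAP 6.1.2 | Arguably a completed visit with 4 days of exposure; the lost-subject rule assumes someone the site has to trace |

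The synopsis label is the odd one out. The instruction in 6.1.2 to find out when participation stopped has no sensible use for someone who came to the clinic.

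**Step 2. Effect on TREF01 if the synopsis rule is applied.** Inputs: 26 enrolled, 13 per arm, 24 completers wanted (protocol 5.7). Let k be the number of late attenders, with nobody else leaving. The documents give no value, so k = 1 to 3 is an assumption. Completers are 26 − k, and the share shown as lost is k/26.

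| k | Completers under the rule | Shown as lost | If late attenders count as completers |
|---|---|---|---|
| 1 | 25 (96.2%) | 1 (3.8%) | 26 (100%), 0 lost |
| 2 | 24 (92.3%) | 2 (7.7%) | 26 (100%), 0 lost |
| 3 | 23 (88.5%) | 3 (11.5%) | 26 (100%), 0 lost |

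Within one arm, each late attender moves 1/13 = 7.7 percentage points, and two in the same arm move 2/13 = 15.4 points.

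**Step 3. What does not change.**

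- *Safety Population and adverse events.* Membership needs one dose, so the subject stays in. Event counts and subject denominators are the same under either label.
- *Exposure.* If participation is taken to stop with the last dosing day, Days 0 to 3 inclusive give 4 days, the same as the completer rule. If the Day 5 attendance date is used, the result is 5 days by subtraction or 6 counting both ends. An arm of 13 has 13 × 4 = 52 subject-days (52/7 = 7.43 subject-weeks). The largest of these readings gives 54 (54/7 = 7.71), a change of 2/52 = 3.8%. The TREF11 note, which uses the actual visit date for completers, opens the same small gap without the label.
- *Day 4 safety tables.* The vital-sign, physical and oral-examination shells draw on named Day 4 eCRF pages, not on a time window.
- *Efficacy.* The FAS morning-after condition already removes the late plaque score, so the ANCOVA has the same subjects either way.

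**The case against.** The strongest defence is context. The sentence follows the statements on not imputing and on missing QHT scores, so it was probably meant as a window for the plaque endpoint. It appears only in the synopses, while the SAP body treats lateness as a deviation and uses loss to follow-up in its ordinary sense. No sentence says that a late attender goes into the early-discontinuation rows. That mapping is inferred from TREF01, which does not cite the 24-hour rule. All of this is fair, and it limits the weight of the point. It does not remove it: a window should be written as a window, the analysis-set definitions already contain one, and the only stated definition of the term is the one that misfires.

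A reader might infer more, and the documents do not support it.

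- *That late attenders would be given one day of exposure.* That default is only for lost subjects who cannot be contacted, and someone who attends has been contacted.
- *That their end-of-study safety data would be lost.* The shells use the Day 4 eCRF pages, and protocol 8.3.2 reports data up to withdrawal even for withdrawn subjects.
- *That two late attenders use up the allowance of 26 − 24 = 2 and so weaken the trial.* The arithmetic is right, but the 12 per arm is justified on QHT. Relabelling the subject as a completer returns no plaque score to the FAS as defined, and drop-outs are not replaced, so the label triggers nothing.

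It can also be objected that counting late attenders as completers has no outer limit. That stands in principle. Showing the actual study day makes any extreme case visible.

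**Conclusion.** The concern holds as a minor inconsistency in the disposition rules. The synopsis sentence classes an examined, possibly fully dosed subject as lost, against SAP 6.1.1, SAP 6.1.2 and TREF18. Followed literally together with TREF01, it would show each late attender as an early discontinuation, at 7.7 percentage points of an arm of 13 or 3.8 points of 26.

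This rests on two assumptions: that the synopsis rule is the one programmed for TREF01, and that at least one subject attends more than 24 hours late. The documents settle neither. With no late attenders the effect is nil. No adverse event count, safety denominator or efficacy estimate is shown to change.

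**What to change.** In both synopses, replace the sentence with: *A subject is lost to follow-up if no end-of-study visit takes place and the subject has not withdrawn.* Withdrawal should be read to include withdrawal by the investigator or sponsor, which TREF01 lists separately. Leave the SAP 6.1.2 exposure rules for contactable and uncontactable lost subjects as they are. The new definition should not require that contact has failed, because 6.1.2 expressly covers lost subjects who are reached.

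Add three statements:

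- A subject who attends the end-of-study visit late is a completer with an out-of-window visit deviation, using the existing TREF18 row. TREF18 is run on the FAS, which as defined excludes this subject, so a footnote should point to listing LREF18 or the table's population should be reconciled with that row.
- The subject's safety data appear with the Day 4 results, with the actual study day shown.
- Use of the late plaque score is decided only by the FAS and PP definitions.

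The cost is one sentence per synopsis, these short additions and a programming note for TREF01. No new data are needed. If the documents are not reissued, SAP section 8 already provides for explaining deviations from the SAP in the statistical analysis report and the clinical study report.
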